1 BACKGROUND AND PROJECT RATIONALE

Metabolic disease including obesity and diabetes has reached epidemic proportions in the past years. Classical risk factors are unhealthy diet and physical inactivity. However, also smoking and air pollution have emerged as unexpected risk factors for type 2 diabetes⁴⁻⁶.

Inflammation has been recognized as key characteristic of metabolic disease and is predictive of future cardiovascular events. In the blood, levels of circulating pro-inflammatory cytokines are elevated^{7,8}. Additionally, macrophages are increased in adipose and muscle tissue of obese subjects^{9,10}, the pancreas of diabetic patients¹¹ and atherosclerotic lesions¹². However, the starting point of chronic low-grade inflammation is not known.

As the gastrointestinal tract first comes into contact with dietary components, but potentially also air pollution/ smoke particles ingested upon mucociliary clearance from the lung, the gut could be the starting point of inflammation in metabolic disease. Indeed, gastrointestinal changes prevail in both metabolic disease by classical risk factors and air pollution, such as altered gut microbiota and increased gut permeability¹³⁻²¹, suggesting that inflammation could start in the gut.

In preclinical studies with mice fed high fat diet, we observed a shift in intestinal macrophages towards pro-inflammatory subpopulations (unpublished). These inflammatory macrophages could potentially initiate systemic/ adipose tissue inflammation and impact thereby on insulin secretion.

The aim of our study is to characterize intestinal macrophages in obese versus lean subjects and smokers versus non-smokers to translate our preclinical findings to human disease and assess whether an inflammatory shift prevails in human intestinal macrophages in metabolic disease. Additionally, to assess whether intestinal macrophage subpopulations can be altered deliberately by nutritional intervention, we will assess intestinal macrophages from subjects scheduled for bariatric surgery that will be on a calorie-restricted diet during the last 4 weeks prior to surgery.

2 PROJECT OBJECTIVES AND DESIGN

2.1 Hypothesis and primary objective

We hypothesize that intestinal macrophages shift towards pro-inflammatory subpopulations in metabolic disease, potentially initiating chronic low-grade inflammation. Additionally, it seems conceivable that a reduction of caloric intake could reverse this inflammatory shift. Regarding air pollution, exposure to particulate matter could also alter intestinal macrophages and thereby mediate metabolic disease.

Thus, our primary objective is to characterize intestinal macrophages in obese versus lean subjects and smokers versus non-smokers and to assess whether intestinal macrophage subpopulations become less pro-inflammatory upon nutritional intervention. To our knowledge, this is first study to comprehensively analyze human intestinal macrophages in metabolic disease.

2.2 Primary and secondary endpoints

Primary endpoints: In our preclinical studies, we found that mice fed a high fat diet had a shift of intestinal macrophages towards inflammatory subpopulations, which precedes adipose tissue inflammation. We think that intestinal macrophages could also be involved in human metabolic disease. Therefore, our primary endpoint is to investigate:

- 1) the frequency & subpopulations of intestinal macrophages from the *colon* in obese versus lean subjects and smokers versus non-smokers,
- 2) the frequency & subpopulations of intestinal macrophages from the *upper gastrointestinal tract* in obese versus lean subjects,
- 3) the frequency & subpopulations of intestinal macrophages from the upper gastrointestinal tract in obese subjects *before and after a nutritional intervention*.

Secondary endpoint: Besides macrophages, also other intestinal immune cells could be implicated in metabolic disease. For example, one preclinical study found that adaptive immunity might be involved²². In case we do not find clear differences in frequency or subpopulations of intestinal macrophages, we will assess other intestinal immune cells (e.g. B-, T-lymphocytes), and enteroendocrine cells (e.g. L-cells) as a secondary endpoint in an explorative manner. Additionally, we aim to correlate our findings from the biopsy samples with inflammation markers and immune cells in the blood, with microbiota and immune cells in the stool and with the eating habits of the patients.

2.3 Project design

This is a prospective, observational study aiming at improving our understanding of the pathophysiology of metabolic disease. The study will entail qualitative and quantitative analyses of patient-derived gut biopsy samples. To our knowledge, this is the first study to comprehensively analyze human intestinal macrophages in metabolic disease.

3 PROJECT POPULATION AND STUDY PROCEDURES

3.1 Project population, inclusion and exclusion criteria

Study population: To elucidate the role of intestinal immune cells in metabolic disease, human gut samples are necessary, which can be obtained from gut biopsies or surgical samples. As patients will undergo diagnostic endoscopy of the gastrointestinal tract or bariatric surgery for clinical reasons and the standard of care will not be changed by the study, there will be no additional interventions to patients by their participation in the study. Participants fulfilling the following inclusion criteria are eligible for the study:

For *colonic tissue samples*, 10 subjects per group referred to the Department of Gastroenterology at the University Hospital Basel or the doctor's office MagenDarm Basel, for a diagnostic colonoscopy on the basis of symptoms suggestive for irritable bowel syndrome or for a screening colonoscopy for colorectal cancer will be included:

- Obese weight non-smokers (BMI >32kg/m²), n=10
- Obese smokers (BMI >32kg/m², ≥1 pack cigarettes/d), n=10
- Normal weight non-smokers (BMI <27kg/m²), n=10
- Normal weight smokers (BMI <27kg/m², ≥1 pack cigarettes/d), n=10

For *tissue samples of the upper gastrointestinal tract and assessment of nutritional intervention*, 10 subjects per group referred to the Department of Visceral Surgery at the University Hospital Basel, the doctor's office MagenDarm Basel or the Department of Visceral Surgery, Hospital Lindenhof Bern, for bariatric surgery will be included. All bariatric patients receive a screening gastroscopy as standard of care prior to the surgery. Subjects willing to participate will contribute gastric and duodenal biopsies from the preoperative screening gastroscopy as well as an approximately 1cm long piece of the jejunum, which is usually disposed during bariatric surgery. As controls, 10 subjects referred to the Department of Gastroenterology at the University Hospital Basel or the doctor's office MagenDarm Basel, for an upper endoscopy on the basis of dyspeptic symptoms will be included as well.

- Obese non-smokers (BMI >35kg/m²) undergoing bariatric surgery, n=10
 - o a) Pre-diet: gastric and duodenal biopsies from the preoperative screening gastroscopy
 - o b) Post-diet: jejunal tissue specimen from bariatric surgery
- Normal weight non-smokers (BMI <27kg/m²), n=10

Patients will be excluded from the study in the following cases: Inability to provide informed consent, e.g. because of mental impairment or insufficient knowledge of project language; intake of corticosteroids, anti-inflammatory/ immunosuppressive drugs potentially altering immune cells; clinical signs of current infection; known anemia (e.g. hemoglobin < 110g/L for males, < 100g/L for females); known neutropenia (e.g. leucocyte count < 1.5 x 10⁹/L or ANC < 0.5 x 10⁹/L); known immunodeficiency, e.g. HIV; known vasculitis, collagenosis; known inflammatory bowel disease; known adrenal insufficiency and/or substitution with glucocorticoids; known clinically significant kidney or liver disease (e.g. creatinine > 1.5mg/dL, AST/ALT > 2 x ULN, alkaline phosphatase > x ULN, or total bilirubin > 1.5 x ULN); risky daily alcohol consumption (> 24g/d for males, > 12g/d for females), known liver cirrhosis Child B or C; known uncontrolled congestive heart failure; known uncontrolled malignant disease; currently pregnant or breastfeeding.

Substudy (validation of diet questionnaire): To validate a diet questionnaire called „Healthy Eating Index“ (modified after J. Russell²³), we will perform a substudy in normal- and overweight people from the Department of Endocrinology (n=100).

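### Previous bariatric surgery, or surgery on the sampled gut segment, is not an exclusion, so operated patients can enter the lean control groups and the obese upper-GI group

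*Combined protocol and SAP*

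**What the plan says.** Section 3.1 of the combined protocol and SAP, repeated in section 4.1, sets six groups of ten by BMI and smoking status, with a referral route for each tissue.

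- **Upper-GI controls:** "Normal weight non-smokers (BMI <27kg/m²), n=10", drawn from patients referred "for an upper endoscopy on the basis of dyspeptic symptoms will be included as well".
- **Upper-GI obese group:** "Obese non-smokers (BMI >35kg/m²) undergoing bariatric surgery, n=10". It supplies "a) Pre-diet: gastric and duodenal biopsies from the preoperative screening gastroscopy" and later a jejunal specimen from the operation. Nothing restricts it to a first bariatric operation.
- **Colon groups:** BMI below 27 or above 32, smokers and non-smokers, from patients with "symptoms suggestive for irritable bowel syndrome or for a screening colonoscopy for colorectal cancer will be included".

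The exclusions, in the same section, open with "Patients will be excluded from the study in the following cases". They cover consent, immune-active drugs, infection, blood counts, immune, renal, hepatic, cardiac and malignant disease, inflammatory bowel disease, alcohol and pregnancy. No item concerns earlier bariatric surgery, or resection or bypass of stomach or bowel. Section 3.2 adds no further filter.

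The data list in section 7.2 names weight, height and BMI and has a general item for other diagnoses of relevance. It has no named item for surgical history or highest past weight.

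Section 2.1 supposes that metabolic disease shifts intestinal macrophages towards inflammatory types, and adds that "it seems conceivable that a reduction of caloric intake could reverse this inflammatory shift".

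**The concern.** The obese-versus-lean contrasts need lean controls whose gut reflects a lean state, and obese subjects whose gut reflects obesity. On the plan's own hypothesis, someone who was obese, had bariatric surgery and now has a BMI below 27 is not a clean example of either state. If the operation involved the stomach, duodenum or jejunum, the sampled tissue may also differ for reasons unrelated to current weight. The same holds for a patient in the obese upper-GI group who is having a repeat operation.

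The protocol already excludes drugs that might change immune cells, and inflammatory bowel disease. Earlier surgery on the sampled organ belongs with these on the same principle, but it is not listed. With ten subjects per group, each such patient is 10% of an arm.

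**Working it through.** **1. Applying the criteria as written.**

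| Hypothetical patient | Group definition | Exclusion list | Result |
|---|---|---|---|
| Earlier bariatric surgery, BMI now below 27, non-smoker, dyspepsia | Meets upper-GI control | No item applies | Eligible as lean control |
| Earlier bariatric surgery, BMI now below 27, screening colonoscopy | Meets a lean colon group (non-smoker, or smoker of at least one pack a day) | No item applies | Eligible as lean control |
| BMI above 35, non-smoker, repeat bariatric operation | Meets upper-GI obese group | No item applies | Eligible as obese |

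The route is open in practice too: section 3.1 names the University Hospital Basel and the same doctor's office as sources of both bariatric patients and upper-GI controls. The protocol gives no time point for BMI. Reading it as BMI at inclusion is an inference, though no passage refers to past weight.

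**2. The plan's own figure.** Section 4.1 gives an effect size of 2.4 (mouse data, subpopulation P1), alpha 0.05, power 0.95, a Mann-Whitney test and 6 per group. Use the noncentral t approximation with n multiplied by the asymptotic relative efficiency 3/π:

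- effective n = 6 × 3/π = 5.73
- noncentrality = 2.4 × √(5.73/2) = 4.06
- degrees of freedom = 2 × 5.73 − 2 = 9.46
- two-sided power = 0.952

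So 6 per group is reproduced. The plan raises it to 10 because it expects more variance in humans than in mice.

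**3. Worst-case dilution.** Let k of the 10 controls be operated patients who each keep a fraction f of the obese shift. The expected mean difference, in SD units, becomes d × (1 − f × k/10). Neither k nor f is in the documents. With f = 1 and k = 1, 2.4 falls to 2.16 and 1.6 falls to 1.44. With f = 0.5 and k = 1, 2.4 falls only to 2.28. With f = 0 there is no dilution.

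Power was simulated at f = 1: normal data, equal SD, exact two-sided Mann-Whitney, 10 v 10, with k control values drawn from the obese distribution. There were 20,000 runs per cell, so the Monte Carlo standard error is at most √(0.25/20,000) = 0.0035.

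| Effect size | k = 0 | k = 1 | k = 2 |
|---|---|---|---|
| 2.4 (planned) | 0.998 | 0.987 | 0.934 |
| 1.6 (assumed) | 0.89 | 0.80 | 0.66 |
| 1.2 (assumed) | 0.67 | 0.55 | 0.43 |

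The lower two rows correspond to the planned mean difference with an SD 1.5 times (2.4/1.6) or 2 times (2.4/1.2) as large. The plan expects more variance but gives no amount.

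**4. What the table leaves out.** It covers only obese-like values among lean controls. It does not model repeat-surgery patients, the before/after comparison, or a direct effect of surgery on macrophages. A direct effect could push the contrast in either direction, and a larger sample would not remove it.

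**The case against.** The strongest reply is that the gap is unlikely to matter much, and most of it stands.

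- **Frequency.** Nothing in the documents shows that even one such patient would be enrolled. An operated patient must have fallen below 27 to be a lean control; a BMI between 27 and 32 fits no colon group, and between 27 and 35 no upper-GI group. Under section 3.2, screening is done by the participating gastroenterologist, endocrinologist or visceral surgeon, who may well know of earlier surgery. However, no written rule tells them to reject the patient.
- **Size.** The simulation lets operated controls keep fully obese-like values. The plan's hypothesis that lower intake may reverse the shift points the other way, so the losses are an upper bound for dilution and not an expected value. At the planned effect, one such control leaves power above 0.95.
- **Recording.** A reader might infer that the study could not capture earlier surgery at all. That goes too far: the general diagnosis item in section 7.2 could hold it. What is missing is a named field and an eligibility rule.
- **Repeat surgery.** The protocol calls this group obese and pre-diet; it never claims the tissue is surgically untouched. No magnitude can be given for this limb.

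What the reply does not remove is the gap itself: the written criteria accept these patients, and no other section closes it.

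**Conclusion.** The concern holds as a minor eligibility gap. The criteria admit previously operated patients both as lean controls and as obese upper-GI subjects, although the plan's own hypothesis treats obesity and reduced intake as altering the cells being measured.

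Its practical size is unknown. The worst-case loss from one operated control in ten is about 1 percentage point of power at the planned effect (0.998 − 0.987 = 0.011) and about 9 points at an assumed effect of 1.6 (0.89 − 0.80). Both rest on normal data, equal SDs and full retention of obese-like values. Bias from the surgery itself is possible in either direction and cannot be sized from the documents.

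Two stronger readings are not supported. One is that the obese-versus-lean comparisons will be materially biased: the documents give no frequency and no effect of surgery. The other is that every earlier gut resection should be barred from all six groups, or that the contrasts should be repeated without formerly obese controls. The argument concerns bariatric surgery and the segment actually sampled. A sensitivity analysis would rest on an undefined label and would shrink arms of ten further.

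**What to change.** Add one item to the exclusion list in section 3.1: previous bariatric surgery (all groups), or previous resection or bypass of the gut segment being sampled. Add a named surgical-history item to the case report form list in section 7.2, so that the rule can be checked for each participant. Highest previous weight may be recorded as well, as an optional and purely descriptive item.

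The cost is one line of eligibility text and one form field, or two with the optional item. A few otherwise eligible patients would not be recruited. The group size of 10 and the planned tests do not change.

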3.3 Study procedures

Screening and inclusion: The study procedure is summarized below. The first patient is planned for September 2018 with a study duration of 2 years. Patients planned for endoscopies of the gastrointestinal tract or bariatric surgeries at the University Hospital Basel, the doctor's office MagenDarm Basel or the Hospital Lindenholz Bern will be screened for inclusion and exclusion criteria and informed about the study by the participating gastroenterologist, endocrinologist or visceral surgeon. Informed consent will be obtained at the latest on the day of the endoscopy or hospital admission for bariatric surgery.

Tissue sampling: Endoscopies or bariatric surgeries will be carried out as per clinical standard of care. Our collaborators are PD Dr. [name] at the Department of Gastroenterology and PD Dr. [name] at the Department of Visceral Surgery, University Hospital Basel, Dr. [name] and [name]. [name] at the doctor's office MagenDarm Basel and PD Dr. [name] at the Department of Visceral Surgery, Hospital Lindenholz Bern. The samples obtained from endoscopies comprise 10 to 12 biopsies per subject including two biopsies being frozen and later on analyzed for inflammatory markers (e.g. TNF α , IL6). The biopsies will be either collected in the Colon transversum in case of colonoscopy or in the stomach and duodenum in case of gastroscopy as we have seen in our mice study different subpopulations depending on the location. The tissue samples from the bariatric surgery are a 1cm piece of the jejunum that would normally be disposed. Additionally, four EDTA and one serum blood tube for the analysis of inflammatory cells and markers in the blood will be taken as well as a single stool sample.

Data: Medical data will be obtained from the patient's electronic health record. The work-up of the tissue specimen, the stool sample and the EDTA blood samples by flow cytometry will be carried out in the laboratory of PD Dr. [name]. Leftover tissue specimen will be snap frozen as well as the serum blood sample after centrifugation. We do not expect biases in our study.

Substudy (validation of diet questionnaire): For validation purposes, normal- and overweight people from the Department of Endocrinology will be asked to fill out a diet questionnaire called „Healthy Eating Index“ (modified after J. Russell) taking about 15 minutes.

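### Primary endpoint 3 compares pre-diet stomach and duodenum with post-diet jejunum, so the planned samples cannot identify a diet effect

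*Combined protocol and SAP*

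**What the plan says.** Section 1 sets the aim "to assess whether intestinal macrophage subpopulations can be altered deliberately by nutritional intervention", using "subjects scheduled for bariatric surgery that will be on a calorie-restricted diet during the last 4 weeks prior to surgery". Section 2.1 carries this into the primary objective: "to assess whether intestinal macrophage subpopulations become less pro-inflammatory upon nutritional intervention". Section 2.2 lists as the third primary endpoint "the frequency & subpopulations of intestinal macrophages from the upper gastrointestinal tract in obese subjects", measured before and after the nutritional intervention.

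The samples are defined in section 3.1 and repeated in section 4.1, for one group of 10 bariatric subjects:

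- "Pre-diet: gastric and duodenal biopsies from the preoperative screening gastroscopy"
- "Post-diet: jejunal tissue specimen from bariatric surgery"

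Section 3.3 confirms that gastroscopy yields stomach and duodenal biopsies and that surgery yields a 1 cm piece of jejunum. The 10 normal-weight controls have an upper endoscopy, so they too give only stomach and duodenum. Sampling is tied to routine care: "there will be no additional interventions to patients by their participation in the study" (section 3.1). Section 3.3 also states "We do not expect biases in our study".

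Section 4.1 names the two-sided Mann-Whitney test at 0.05. It describes no analysis specific to the before/after comparison and no adjustment for site or specimen type.

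**The concern.** A before/after comparison can say something about diet only if the tissue compared is otherwise alike, or if a comparator shows what the other differences contribute. Here every pre-diet observation is an endoscopic biopsy of stomach or duodenum, and every post-diet observation is a surgical piece of jejunum. The diet fills the last 4 weeks before surgery, so the two samples are also at least 4 weeks apart; the plan does not state the interval.

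A difference between gut sites or specimen types could be reported as a diet effect, and an opposing difference could hide a real one. At stake are one of three primary endpoints and a named part of the primary objective.

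**Working it through.** **1. The plan's own figure.** Section 4.1 gives effect size 2.4, alpha 0.05, power 0.95 and 6 per group. For a two-sided Mann-Whitney test with normal data, the effective group size is 6 × 3/π = 5.73. The degrees of freedom are 2 × 5.73 − 2 = 9.46 and the noncentrality is 2.4 × √(5.73/2) = 4.06. Power is 0.952, so 6 per group reproduces. The problem is not one of sample-size arithmetic.

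**2. What is sampled in the upper-gut part** (sections 3.1 and 3.3), coded for an additive model with duodenum as the reference site:

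| Cell | Intercept | Obesity | Stomach | Jejunum | Diet |
|---|---|---|---|---|---|
| Lean, stomach | 1 | 0 | 1 | 0 | 0 |
| Lean, duodenum | 1 | 0 | 0 | 0 | 0 |
| Obese pre-diet, stomach | 1 | 1 | 1 | 0 | 0 |
| Obese pre-diet, duodenum | 1 | 1 | 0 | 0 | 0 |
| Obese post-diet, jejunum | 1 | 1 | 0 | 1 | 1 |

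The jejunum and diet columns are identical, so the rank is 4 for 5 parameters. The available contrasts are:

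- obese minus lean, within stomach or within duodenum = obesity (estimable);
- post-diet jejunum minus pre-diet duodenum = jejunum + diet (only the sum);
- post-diet jejunum minus pre-diet stomach = jejunum − stomach + diet (again inseparable).

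Specimen type, elapsed time and surgical setting each repeat the same column. Adding specimen type gives rank 4 of 6; adding all three gives 4 of 8. These larger models restate the first result and are not further evidence.

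**3. Possible escapes.**

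- *Duodenum only:* three cells and four parameters (intercept, obesity, jejunum, diet) give rank 3; diet is still not estimable.
- *Dropping additivity:* this does not help, because the only post-diet cell shares its site with no other cell.
- *Larger sample or paired test:* the expected difference is still diet plus everything that changes with it.

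**4. Illustration of the consequence.** The documents give no human site effect and no within-subject correlation, so both are assumed here. The plan does not name the pre-diet comparator site, so pre-diet tissue is treated as one sample. The diet effect is set to zero, data are normal, there are 10 samples per time point, and the exact two-sided Mann-Whitney test rejects if U ≤ 23 or U ≥ 77.

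| Assumed site/specimen shift | p<0.05, independent samples | Range, correlation 0 to 0.7 |
|---|---|---|
| 0 | 4.3% | 0.2–4.3% |
| 0.5 SD | 16.2% | 7–16% |
| 1.0 SD | 51.4% | 51–54% |
| 1.5 SD | 85.2% | 85–94% |

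A signed-rank test, which respects the pairing, gives 16–29%, 49–79% and 83–99% at shifts of 0.5, 1.0 and 1.5 SD (correlation 0 to 0.5). Pairing does not remove the problem.

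**The case against.** The study is observational and uses tissue that routine care yields. Endpoint 3 is worded as an investigation and the diet hypothesis only as conceivable. All three sites belong to the upper gastrointestinal tract, and the bias may be small. The location remark in section 3.3 comes from mice, may refer to colon versus upper gut, and gives no duodenum–jejunum contrast. The documents do not show that specimen type, time or surgical setting alters the readout. The simulated shifts are invented, and independent samples do not match a design that uses the same 10 subjects twice. Section 4.1 illustrates the Mann-Whitney test only with between-group comparisons, so applying it to endpoint 3 is partly inferred.

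Much of this stands as a limit on what can be said about size. The bias cannot be quantified, specimen type, time and setting are possible rather than demonstrated components, and the simulation is illustration only. None of it restores identification. A shared anatomical label does not make the sites equivalent, and nothing in the design could show that the bias is small. Limited tissue explains the sampling but does not license attribution to diet, which the aims in sections 1 and 2.1 make while section 2.2 ranks the comparison as primary.

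**Conclusion.** The concern holds. Diet is completely aliased with gut site and with everything else that differs between gastroscopy and surgery. The planned samples give one composite contrast, whatever the sample size or test. This rests only on the sampling layout in sections 3.1, 3.3 and 4.1 and needs no assumed effect size. Describing the two sets of samples remains possible; attributing their difference to diet does not. The assurance in section 3.3 that no bias is expected is wrong for this comparison.

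Endpoint 1 is not affected by this problem. Endpoint 2 is not affected if it uses stomach and duodenum in both groups. This must be corrected, because a primary endpoint and part of the primary objective cannot be answered as written.

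**What to change.** Text changes only:

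- **Section 1:** replace the aim of testing deliberate alteration by diet with: *As an exploratory description, we will compare macrophages in jejunal tissue taken after the preoperative diet with those in stomach and duodenal biopsies taken before it.*
- **Section 2.1:** remove the nutritional-intervention clause from the primary objective.
- **Sections 2.2 and 4.1:** reclassify endpoint 3: *Exploratory: macrophage frequency and subpopulations in post-diet jejunum versus pre-diet stomach/duodenum in obese subjects. Site, specimen type, time and surgical setting change together with diet, so this comparison cannot support a conclusion that diet alters intestinal macrophages.*
- **Section 3.3:** replace the bias sentence with: *In the before/after comparison, diet is confounded with gut site, specimen type, time and surgical setting; the size and direction of this bias are unknown.*
- **Editorial:** state in section 2.2 that endpoint 2 uses stomach and duodenum only, and bring the subheadings in sections 3.1 and 4.1 that mention assessing the nutritional intervention into line.

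The cost is one less favourable primary claim. Because a primary endpoint and objective change, section 5.4 may require Ethics Committee approval before implementation. No patients or procedures are added.

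An extra linking sample is not proposed. A post-diet duodenal biopsy taken outside surgery would identify only diet plus elapsed time, unless time has no effect. Taken at surgery, it would add the surgical setting to that sum. It would also go beyond the routine-care premise of sections 3.1 and 6.1; whether to consider it is for the sponsor.
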